### **3. INTRODUCTION**

This SAP has been developed after review of the Clinical Study Protocol (final version dated 13 March 2019) and Protocol Amendment (a) (final version dated 14 February 2020).

This SAP describes the planned analysis of the safety, tolerability, pharmacokinetic (PK), pharmacodynamic (PD), and efficacy data from this study. A detailed description of the planned TFLs to be presented in the clinical study report (CSR) is provided in the accompanying TFL shell document.

The intent of this document is to provide guidance for the statistical and PK analyses of data. In general, the analyses are based on information from the protocol, unless they have been modified by agreement with Eli Lilly and Company. A limited amount of information concerning this study (e.g., objectives, study design) is given to help the reader's interpretation. When the SAP and TFL shells are agreed upon and finalized, they will serve as the template for this study's CSR.

This SAP supersedes the statistical considerations identified in the protocol; where considerations are substantially different, they will be so identified. If additional analyses are required to supplement the planned analyses described in this SAP, they may be performed and will be identified in the CSR. Any substantial deviations from this SAP will be agreed upon with Eli Lilly and Company and identified in the CSR. Any minor deviations from the TFLs may not be documented in the CSR.

This SAP is written with consideration of the recommendations outlined in the International Conference on Harmonisation (ICH) E9 Guideline entitled Guidance for Industry: Statistical Principles for Clinical Trials and the ICH E3 Guideline entitled Guidance for Industry: Structure and Content of Clinical Study Reports.

### **4. STUDY OBJECTIVES**

#### **4.1 Primary Objective**

To investigate the safety and tolerability of tirzepatide after multiple subcutaneous (SC) doses administered to Chinese patients with Type 2 Diabetes Mellitus (T2DM).

#### **4.2 Secondary Objective**

To characterize the PK of tirzepatide after multiple SC doses in Chinese patients with T2DM.

[figure not shown]
#### **4.3 Exploratory Objectives**

- To investigate the efficacy of tirzepatide after multiple SC doses administered to Chinese patients with T2DM
- To investigate the exploratory PD effects of tirzepatide after multiple SC doses administered to Chinese patients with T2DM
- To evaluate the formation of anti-drug antibodies (ADAs) to tirzepatide after multiple SC doses administered to Chinese patients with T2DM

## 5. STUDY DESIGN

Study GPHT is a Phase 1, single-site, patient- and investigator-blind, placebo-controlled, randomized, multiple dose titration study in Chinese patients with T2DM.

Figure 1 illustrates the study design.

Abbreviations: LY = tirzepatide; PL = placebo; QW = once weekly.

### Figure 1. Illustration of study design

Patients will be administered either 16 or 24 weekly SC doses of tirzepatide or placebo.

#### Screening (Visit 1)

The purpose of screening procedures at Visit 1 is to establish initial eligibility and to obtain blood samples for laboratory assessments needed to confirm eligibility at Visit 2. Before performing any study procedures, the patient will sign the informed consent form.

#### Lead-in (Visit 2 to Visit 3)

At Visit 2, patients and their caregiver(s), if applicable, will receive a glucometer, study diaries, and training on how to perform self-monitoring of plasma glucose (PG) and record blood glucose values, hypoglycemic events, medications, and adverse events (AEs). Patients will also be trained on disease management and study procedures; this training can be repeated at subsequent visits as deemed appropriate.

Patients will conduct the 7-point self-monitored plasma glucose (7p-SMPG) approximately every 3 days since Day -13 during the lead-in period and will record readings in patient diary. Prior oral antidiabetic medication (OAM) should be discontinued during the lead-in period. Additionally, site personnel will require patients who were taking OAM at screening to monitor their PG in the morning before breakfast during the lead-in period.

## **Treatment Period**

### **Cohort 1**

Patients in Cohort 1 will receive either tirzepatide with titration regimen starting from 2.5 mg for Weeks 0 through 3 followed by 5 mg for Weeks 4 through 7, 7.5 mg for Weeks 8 through 11, and 10 mg for Weeks 12 through 15, or corresponding volume-matched placebo. During clinical research unit (CRU) visits 3a, 4, 5, 6a, 7, 8, 9, 10 and 11a, site staff will administer SC doses of tirzepatide or placebo. Patients may either self-administer or visit the CRU to have staff administer SC doses of tirzepatide or placebo at the beginning of Weeks 2, 3, 5, 6, 9, 10, and 11.

### **Cohort 2**

Patients in Cohort 2 will receive either tirzepatide with titration regimen starting from 2.5 mg for Weeks 0 through 3 followed by 5 mg for Weeks 4 through 7, 7.5 mg for Weeks 8 through 11, 10 mg for Weeks 12 through 15, 12.5 mg for Weeks 16 through 19, and 15 mg for Weeks 20 through 23, or corresponding volume-matched placebo. During CRU visits 3a, 4, 5, 6a, 7, 8, 9, 10, 11, 12 and 13a, site staff will administer SC doses of tirzepatide or placebo. Patients may either self-administer or visit the CRU to have staff administer SC doses of tirzepatide or placebo at the beginning of Weeks 2, 3, 5, 6, 9, 10, 11, 13, 14, 15, 17, 18, and 19.

## **Follow-Up Period**

Visits for safety follow-up and PK sampling will occur on 2 separate visits. These visits will be approximately 7 and 28 days after the last dose of investigational product (IP).

## **6. TREATMENTS**

The following is a list of the study treatment labels that will be used in the safety, PD, and efficacy TFLs.

Cohort	Study Treatment Name	Treatment order in TFL
All	Placebo QW SC	1
1	2.5-10 mg tirzepatide QW SC*	2
2	2.5-15 mg tirzepatide QW SC**	3

Abbreviations: QW = once weekly; SC = subcutaneous

\* Patients receive 2.5 mg for Weeks 0 through 3, 5 mg for Weeks 4 through 7, 7.5 mg for Weeks 8 through 11, and 10 mg for Weeks 12 through 15

\*\* Patients receive 2.5 mg for Weeks 0 through 3, 5 mg for Weeks 4 through 7, 7.5 mg for Weeks 8 through 11, 10 mg for Weeks 12 through 15, 12.5 mg for Weeks 16 through 19, and 15 mg for Weeks 20 through 23

The following is a list of the study treatment labels that will be used in the PK TFLs, where a full profile is collected.

Cohort	Study Treatment Name	Treatment order in TFL
1	2.5 mg tirzepatide QW SC	1
	5 mg tirzepatide QW SC	2
	10 mg tirzepatide QW SC	3
2	2.5 mg tirzepatide QW SC	4
	5 mg tirzepatide QW SC	5
	15 mg tirzepatide QW SC	6

Abbreviations: QW = once weekly; SC = subcutaneous

For predose (trough) PK samples, the treatment labels will be consistent with the safety, PD and efficacy TFLs.

## 7. SAMPLE SIZE JUSTIFICATION

The sample size for the study was chosen to provide sufficient data to evaluate the primary objective of this study and is not intended to achieve any priori statistical requirements.

Approximately 24 Chinese patients with T2DM may be enrolled so that approximately 16 patients complete the study with compliant defined dosing regimen. Patients will be administered either 16 (Cohort 1) or 24 (Cohort 2) weekly SC doses of tirzepatide or placebo in a ratio of 10 tirzepatide:2 placebo for both cohorts.

Replacement of discontinued patients is not planned because the sample size is determined considering the expected drop-out rate.

## 8. DEFINITION OF ANALYSIS POPULATIONS

Safety analyses will be conducted for all enrolled patients, whether or not they completed all protocol requirements.

The Pharmacokinetic population will consist of all patients who received at least 1 dose of the IP and have evaluable PK data.

The Pharmacodynamic population will consist of all patients who received at least 1 dose of the IP and have evaluable PD data.

The Efficacy population will consist of all patients who received at least 1 dose of the IP and have evaluable efficacy data.

All protocol deviations that occur during the study will be considered for their severity/impact and will be taken into consideration when subjects are assigned to analysis populations.

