**Table GPHT.1. Objectives and Endpoints**

Primary Objectives	Endpoints
To investigate the safety and tolerability of tirzepatide after multiple SC doses administered to Chinese patients with T2DM	Incidence of TEAEs
Secondary Objectives	Endpoints
To characterize the PK of tirzepatide after multiple SC doses in Chinese patients with T2DM	AUC and $C_{\max}$ of tirzepatide
Exploratory Objectives	Endpoints
To investigate the efficacy of tirzepatide after multiple SC doses administered to Chinese patients with T2DM	Hemoglobin A1c, body weight, fasting plasma glucose levels, 7p-SMPG
To investigate the exploratory PD effects of tirzepatide after multiple SC doses administered to Chinese patients with T2DM	Lipids, subjective appetite sensation (VAS)
To evaluate the formation of ADAs to tirzepatide after multiple SC doses administered to Chinese patients with T2DM	Presence of ADAs to tirzepatide

[figure not shown]
Abbreviations: ADA = antidrug antibody; AUC = area under the concentration-time curve;  $C_{\max}$  = maximum observed drug concentration; PD = pharmacodynamic; PK = pharmacokinetics; SC = subcutaneous; 7p-SMPG = 7-point self-monitored plasma glucose; T2DM = type 2 diabetes mellitus; VAS = visual analogue scale.

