### **Treatment Period**

Patients will be admitted to the clinical research unit (CRU) on Day -1. If the investigator decides not to administer the first dose to a patient on a particular day based on the results of medical assessments, vital signs, or electrocardiograms (ECGs), the patient's visit may be rescheduled, and any procedures performed up to that point may be repeated.

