CRP	clinical research physician: Individual responsible for the medical conduct of the study. Responsibilities of the CRP may be performed by a physician, clinical research scientist, global safety physician, or other medical officer.
CRS	clinical research scientist
CRU	clinical research unit
CT	computed tomography
DPP	dipeptidyl peptidase
ECG	electrocardiogram
eCRF	electronic case report form
eGFR	estimated glomerular filtration rate
enroll	The act of assigning a patient to a treatment. Patients who are enrolled in the study are those who have been assigned to a treatment.
enter	Patients entered into a study are those who sign the informed consent form directly or through their legally acceptable representatives.
ERB	ethical review board
FSH	follicle-stimulating hormone
GCP	good clinical practice
GI	gastrointestinal
GIP	glucose-dependent insulinotropic polypeptide
GLP-1	glucagon-like peptide-1
HbA1c	hemoglobin A1c
HIV	human immunodeficiency virus

IB	Investigator's Brochure
ICF	informed consent form
ICH	International Council for Harmonisation
informed consent	A process by which a patient voluntarily confirms his or her willingness to participate in a particular study, after having been informed of all aspects of the study that are relevant to the patient's decision to participate. Informed consent is documented by means of a written, signed, and dated informed consent form.
investigational product (IP)	A pharmaceutical form of an active ingredient or placebo being tested or used as a reference in a clinical study, including products already on the market when used or assembled (formulated or packaged) in a way different from the authorized form, or marketed products used for an unauthorized indication, or marketed products used to gain further information about the authorized form.
investigator	A person responsible for the conduct of the clinical study at a study site. If a study is conducted by a team of individuals at a study site, the investigator is the responsible leader of the team and may be called the principal investigator.
IWRS	interactive web-response system
legal representative	An individual or judicial or other body authorized under applicable law to consent, on behalf of a prospective patient, to the patient's participation in the clinical study.

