## 9.6 Safety and Tolerability Assessments

### 9.6.1 Adverse events

Where changes in severity are recorded in the Case Report Form (CRF), each separate severity of the AE will be reported in the listings, only the most severe will be used in the summary tables. A pre-existing condition is defined as an AE that starts before the subject has provided written informed consent and is ongoing at consent. A non-treatment emergent AE is defined as an AE which starts after informed consent but prior to dosing. A treatment-emergent AE is defined as an AE which occurs postdose or which is present prior to dosing and becomes more severe postdose.

All AEs will be listed. Treatment-emergent AEs will be summarized by treatment, severity and relationship to the study drug. The frequency (the number of AEs, the number of subjects experiencing an AE and the percentage of subjects experiencing an AE) of treatment-emergent AEs will be summarized by treatment, Medical Dictionary for Regulatory Activities (MedDRA) version 22.1 system organ class and preferred term. The summary and frequency AE tables will be presented for all causalities and those considered related to the study drug by the investigator. Any serious AEs will be listed. AEs by week of onset will be presented.

Discontinuations due to AEs will be listed.

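### The safety set counts every randomized patient, dosed or not, so a never-dosed patient would lower the primary TEAE incidence

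*SAP*

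**What the plan says.** SAP Section 8 sets the safety analysis on enrolment: "Safety analyses will be conducted for all enrolled patients, whether or not they completed all protocol requirements". Protocol Section 10.3 and the Statistical Analysis paragraph of the protocol synopsis carry the same rule. Protocol Appendix 1 fixes what enrolled means: "Patients who are enrolled in the study are those who have been assigned to a treatment". Receiving a dose is not part of that definition.

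The other three populations in SAP Section 8 do require a dose. For PK: "The Pharmacokinetic population will consist of all patients who received at least 1 dose of the IP and have evaluable PK data". The PD and efficacy populations are built the same way.

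The primary endpoint in protocol Table GPHT.1 is "Incidence of TEAEs". SAP 9.6.1 defines the event: "A treatment-emergent AE is defined as an AE which occurs postdose or which is present prior to dosing and becomes more severe postdose". The planned TEAE tables, by treatment, give the number of events, "the number of subjects experiencing an AE and the percentage of subjects experiencing an AE".

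On timing, protocol Section 7.2 places randomization at Visit 3a, and the Schedule of Activities puts randomization and the first dose on that same Day 1 visit. The Treatment Period text in protocol Section 5.1 covers a withheld first dose, beginning: "If the investigator decides not to administer the first dose to a patient on a particular day". It goes on to say that the visit may be rescheduled and procedures repeated.

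**The concern.** The numerator and denominator of the primary endpoint rest on different conditions. The numerator needs a dose; the denominator needs only a treatment assignment. A patient with an assignment and no dose can only lower the reported percentage. SAP 9.6.1 would class any event such a patient had after consent as non-treatment-emergent.

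The safety set carries the primary endpoint, yet it is the only one of the four sets without a minimum-dose condition, and no reason is given. The treatment groups are small enough for a single patient to move a percentage visibly. A shift in one group and not the other would also affect the descriptive comparison between tirzepatide and placebo. Other subject percentages computed on this set, such as those for the hypoglycemia categories in SAP 9.6.2, would be affected in the same way.

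**Working it through.** **Step 1. Group sizes.** The synopsis plans two cohorts of about 12, each allocated 10 tirzepatide to 2 placebo. 2 × (10 + 2) = 24, which reproduces the planned enrolment of approximately 24. The treatment table in SAP Section 6 has one column for each tirzepatide cohort and one placebo column for all cohorts, so the planned denominators are 10, 10 and 2 + 2 = 4.

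**Step 2. Does any rule remove an undosed patient?** The one candidate is the closing sentence of SAP Section 8, under which protocol deviations are considered when patients are assigned to populations. It contains no dosing rule. A first dose withheld as protocol Section 5.1 allows need not be a deviation. So no stated rule takes the patient out of the safety set.

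**Step 3. Formula.** Let N be the patients assigned to a group, u those never dosed, and x those with a TEAE (x cannot exceed N − u).

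- Incidence on all enrolled: x/N
- Incidence on all dosed: x/(N − u)
- Ratio of enrolled to dosed: (N − u)/N
- Difference: x/(N − u) − x/N = x·u / [N(N − u)]

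**Step 4. Numbers.** The documents give neither u nor a TEAE rate. I take u from 0 to 2 and the values of x below as assumptions.

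| Group | u | Ratio | x | On dosed | On enrolled | Difference (points) |
|---|---|---|---|---|---|---|
| Tirzepatide cohort, N = 10 | 1 | 9/10 = 0.90 | 1 | 1/9 = 11.1% | 1/10 = 10.0% | 1.1 |
| | 1 | 0.90 | 5 | 5/9 = 55.6% | 5/10 = 50.0% | 5.6 |
| | 1 | 0.90 | 9 | 9/9 = 100% | 9/10 = 90.0% | 10.0 |
| | 2 | 8/10 = 0.80 | 4 | 4/8 = 50.0% | 4/10 = 40.0% | 10.0 |
| Pooled placebo, N = 4 | 1 | 3/4 = 0.75 | 1 | 1/3 = 33.3% | 1/4 = 25.0% | 8.3 |
| | 1 | 0.75 | 3 | 3/3 = 100% | 3/4 = 75.0% | 25.0 |
| | 2 | 2/4 = 0.50 | 1 | 1/2 = 50.0% | 1/4 = 25.0% | 25.0 |

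With u = 0 the ratio is 1 and nothing changes.

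**Step 5. Standing of the placebo rows.** The pooling sentence in protocol Section 10.3 refers to patients who got placebo, not those assigned to it. On that wording, a patient assigned to placebo but never dosed might fall outside the pooled column. The placebo rows therefore hold only if the patient is counted there.

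**The case against.** The strongest reply is that the case may never arise. Randomization and first dose share one inpatient visit. Vital signs and ECG are scheduled on Day -1 and again predose on Day 1, so a decision to withhold the dose can precede randomization. A reader might infer from protocol Section 5.1 that the plan expects some randomized patients never to be treated. It does not say so: the text describes postponement. What remains is that rescheduling is permitted rather than guaranteed, and no passage requires the predose checks to be cleared before randomization.

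Second, any dilution would be visible and reversible. Subject counts appear beside the percentages, disposition is listed (SAP 9.2), and protocol Section 10.2.1 requires the extent of participation of each discontinued patient to be reported. SAP 9.6.14 plans no inferential safety analysis and the sample size has no statistical target, so no test, error rate or decision rule is touched. All of this stands, and it limits the point to a small improvement.

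Third, an all-enrolled set has a rationale: protocol Section 10.3.1.1 also covers events related to protocol procedures, which an undosed patient can have. That is fair, and all-enrolled is not an error in itself. But SAP 9.6.1 already lists all AEs, so those events can be kept without holding the patient in the TEAE denominator.

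Finally, a reader might infer that the protocol-deviation sentence in SAP Section 8 contradicts keeping non-completers in the safety set. The documents do not support that. The sentence only says that deviations are considered; it orders no safety exclusion, and the two statements can be read together.

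**Conclusion.** The point holds in conditional form. As written, a randomized patient who never receives a dose counts in the denominator of the primary TEAE incidence and cannot count in the numerator, and no stated rule removes that patient.

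For one such patient, which is an assumption, the reported incidence in a tirzepatide cohort is multiplied by 0.90, a loss of 1.1 to 10.0 percentage points depending on how many of the 9 dosed patients have a TEAE. The placebo factor of 0.75 is the larger effect but the less secure one. A reader might infer that the placebo rate would certainly be understated by a quarter; the pooling sentence in protocol Section 10.3 leaves open whether the patient would be in that column at all.

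The expected number of such patients is small and may be zero, in which case the enrolled and dosed sets coincide. This is a cheap improvement to a descriptive analysis and does not threaten the study's conclusions.

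**What to change.** In SAP Section 8, define the safety population as all randomized patients who received at least one dose of IP. Show randomized-not-dosed patients in the disposition listing, and keep any procedure-related AEs they have in the AE listings, so that no information is lost. The placebo pooling wording in protocol Section 10.3 then agrees with the denominator, and the ambiguity over the placebo column goes.

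The cost is one definition and one entry in SAP Section 11, which now states that nothing differs from the protocol. SAP Section 3 lets the SAP supersede the protocol's statistical considerations where differences are identified, so the analysis can be set there. The matching sentences in protocol Section 10.3 and the synopsis can be aligned at the next amendment. The downside is a recorded departure from the protocol wording until then. In return, the primary denominator is settled in advance rather than after a case has arisen.

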## **9. STATISTICAL METHODOLOGY**

### **9.1 General**

Data listings will be provided for all data that is databased. Summary statistics and statistical analysis will only be presented for data where detailed in this SAP. For continuous data, summary statistics will include the arithmetic mean, arithmetic standard deviation (SD), median, min, max and n; for log-normal data (e.g. the PK parameters: area under the concentration-time curve [AUC] and Maximum observed drug concentration [ $C_{max}$ ]) the geometric mean and geometric coefficient of variation (CV%) will also be presented. For categorical data, frequency count and percentages will be presented. Data listings will be provided for all subjects up to the point of withdrawal, with any subjects excluded from the relevant population highlighted. Summary statistics and statistical analyses will generally only be performed for subjects included in the relevant analysis population. For the calculation of summary statistics and statistical analysis, unrounded data will be used.

Mean change from baseline is the mean of all individual subjects' change from baseline values. Each individual change from baseline will be calculated by subtracting the individual subject's baseline value from the value at the timepoint. The individual subject's change from baseline values will be used to calculate the mean change from baseline using a SAS procedure such as Proc Univariate.

Data analysis will be performed using SAS® Version 9.4 or greater.

### **9.2 Demographics and Subject Disposition**

Subject disposition will be listed.

The demographic variables age, sex, race, ethnicity, body weight, height, body mass index, hemoglobin A1c (HbA1c), duration of diabetes and OAM use will be summarized and listed. All other demographic variables will be listed only.

### **9.3 Pharmacokinetic Assessment**

#### **9.3.1 Pharmacokinetic Analysis**

Noncompartmental methods applied with a validated software program (Phoenix WinNonlin Version 8.1 or later) to the plasma concentrations of tirzepatide will be used to determine the following pharmacokinetic parameters, when possible, on Days 1 (Week 0), 50 (Week 7), 106 (Week 15 [Cohort 1 only]) and 162 (Week 23 [Cohort 2 only]):

Parameter	Units	Definition
AUC(0-168)	ng.h/mL	area under the concentration versus time curve from time zero to 168 hour postdose
C max	ng/mL	maximum observed drug concentration
t max	h	time of maximum observed drug concentration
t 1/2	h	half-life associated with the terminal rate constant ( $\lambda_z$ ) in non-compartmental analysis
CL/F	L/h	apparent total body clearance of drug calculated after extra-vascular administration
V ss /F	L	apparent volume of distribution as steady state after extravascular administration
V z /F	L	apparent volume of distribution during the terminal phase after extra-vascular administration

Additional pharmacokinetic parameters may be calculated, as appropriate. The software and version used for the final analyses will be specified in the clinical study report. Any exceptions or special handling of data will be clearly documented within the final study report.

Formatting of tables, figures and abbreviations will follow the Eli Lilly Global PK/PD/TS Tool: NON-COMPARTMENTAL PHARMACOKINETIC STYLE GUIDE. The version of the tool effective at the time of PK analysis will be followed.

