explore alternative titration schemes (longer time intervals between dose escalations and different dose escalations) to support evaluation of optimised dosing regimen(s) in Phase 3. Study GPGF demonstrated that a longer time between dose increases and/or smaller dose escalations are better tolerated than rapid or large step-size dose escalations, as indicated by lower frequency of GI tolerability AEs and fewer patients discontinuing treatment compared to the data observed in Study GPGB.

In addition, the safety, tolerability, and PK/PD of tirzepatide are being evaluated in the ongoing Study GPGC; a Phase 1, 8-week multiple ascending dose (MAD) study in Japanese patients with T2DM. This study involves a comparison of 3 once-weekly SC dose levels of tirzepatide (2.5 mg to 10 mg titration regimen for Cohort 1; 5 mg to 15 mg titration regimen for Cohort 2; and 5 mg fixed dose for Cohort 3), or placebo. The safety and tolerability data of Study GPGC supports the use of doses up to 15 mg of tirzepatide in Japanese patients.

Tirzepatide PK was studied across a range of doses administered as single doses or multiple doses via a once-weekly dosing regimen. Based on the cumulative data to date, tirzepatide PK appeared linear and dose proportional during the dose range studied. Peak concentrations were observed at 1 to 2 days postdose, and the half-life was approximately 5 days.

In summary, the data from Study GPGB and Study GPGF support continued development of tirzepatide as a treatment for T2DM. Lilly proposes to conduct five Phase 3 randomised, controlled glycaemic-control trials. The doses selected for this study are 2.5, 5, 7.5, 10, 12.5, and 15 mg, which will be administered in a dose-escalation scheme that uses 2.5-mg dose increments and 4-week intervals.

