**Table GPHT.2. Tirzepatide Treatment Regimens**

Cohort	Treatment Period Interval					
	Weeks	Weeks	Weeks	Weeks	Weeks	Weeks
	0 to 3	4 to 7	8 to 11	12 to 15	16 to 19	20 to 23
1	2.5 mg	5 mg	7.5 mg	10 mg		
2	2.5 mg	5 mg	7.5 mg	10 mg	12.5 mg	15 mg

Note: All doses will be administered once weekly using a single-dose pen.

All injections will be administered into the SC tissue of the abdominal wall. Injection sites will be alternated weekly between 4 sites on the abdominal wall (that is, right and left upper quadrants and right and left lower quadrants). During CRU visits as shown in the Schedule of Activities, Section 2, site staff will administer SC doses of tirzepatide or placebo. For dosing at non-CRU visits, patients may either self-administer or visit the CRU to have staff administer SC doses of tirzepatide or placebo.

The investigator or designee is responsible for

- explaining the correct use of the IP to the site personnel and the patient
- verifying that instructions are followed properly
- maintaining accurate records of IP dispensing and collection
- instructing patients to discard all used single-dose pens (SDPs) for tirzepatide in a closeable, puncture-resistant container and dispose according to local regulations

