### **10.3.3. Pharmacokinetic Analyses**

#### **10.3.3.1. Pharmacokinetic Parameter Estimation**

Pharmacokinetic parameter estimates for tirzepatide will be calculated using standard noncompartmental methods of analysis.

The primary parameters for analysis will be maximum drug concentration ( $C_{max}$ ), area under the concentration-time curve (AUC), and time to  $C_{max}$  ( $T_{max}$ ) of tirzepatide. Other

noncompartmental parameters, such as half-life, apparent clearance, and apparent volume of distribution may be reported. Model-based analysis may be performed combined with data from other studies.

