### General PK Parameter Rules

- Actual sampling times will be used in the final analyses of individual PK parameters, except for non-bolus pre-dose sampling times which will be set to zero.
- Cmax and tmax will be reported from observed values. If Cmax occurs at more than one timepoint, tmax will be assigned to the first occurrence of Cmax.
- AUC parameters will be calculated using a combination of the linear and logarithmic trapezoidal methods (linear-log trapezoidal rule). The linear trapezoidal method will be applied up to tmax and then the logarithmic trapezoidal method will be used after tmax. The minimum requirement for the calculation of AUC will be the inclusion of at least three consecutive plasma concentrations above the lower limit of quantification (LLOQ), with at least one of these concentrations following Cmax.
- Half-life (t1/2) will be calculated, when appropriate, based on the apparent terminal log-linear portion of the concentration-time curve. The start of the terminal elimination phase for each subject will be defined by visual inspection and generally will be the first point at which there is no systematic deviation from the log-linear decline in plasma concentrations. Half-life will only be calculated when a reliable estimate for this parameter can be obtained comprising of at least 3 data points. If t1/2 is estimated over a time window of less than 2 half-lives, the values will be flagged in the data listings. Any t1/2 value excluded from summary statistics will be documented in the footnote of the summary table.

- A uniform weighting scheme will be used in the regression analysis of the terminal log-linear portion of the concentration-time curve.
- The parameters based on predicted last quantifiable drug concentration ( $C_{last}$ ) will be reported.

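### SAP 9.3.1 lists Vss/F with no formula in a study with subcutaneous dosing only, so the tabulated value would include absorption time and would not be the steady-state volume it is labelled as

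*SAP*

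**What the plan says.** The parameter table in SAP 9.3.1 includes Vss/F, in litres, defined as "apparent volume of distribution as steady state after extravascular administration", alongside CL/F and the terminal-phase volume Vz/F. These are to be determined "when possible, on Days 1 (Week 0), 50 (Week 7), 106 (Week 15 [Cohort 1 only]) and 162 (Week 23 [Cohort 2 only". SAP 9.3.2 has all PK parameters listed and summarised by treatment and profile day.

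The only AUC in the table is the "area under the concentration versus time curve from time zero to 168 hour postdose". The general rules cover the trapezoidal method ("AUC parameters will be calculated using a combination of the linear and logarithmic trapezoidal methods") and the extrapolation basis ("The parameters based on predicted last quantifiable drug concentration" are reported). They give no formula for Vss/F. MRT, the area under the first-moment curve (AUMC) and AUC to infinity are not listed. Nothing says whether a single-dose or a steady-state form applies after Day 1.

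On route, Protocol 7.1 states: "All injections will be administered into the SC tissue of the abdominal wall". No arm or regimen includes an intravenous dose.

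The protocol asks for less than the SAP. Section 10.3.3.1 says only that parameters such as half-life, "apparent clearance, and apparent volume of distribution may be reported". It does not name Vss/F. The PK endpoints in Table GPHT.1 are AUC and Cmax.

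**The concern.** Steady-state volume equals clearance times the mean residence time of disposition. Noncompartmental analysis of a subcutaneous profile does not give that residence time. It gives disposition time plus mean absorption time, and separating the two needs an intravenous reference or a model outside noncompartmental analysis. CL/F times the observed residence time is therefore not Vss/F. Longer sampling would not remove the absorption term, and neither do the follow-up samples up to 35 days after the last dose (Day 106 to 141; Day 162 to 197).

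What is at stake is a number in the PK tables that does not mean what its label says. Because the SAP does not define the calculation, a reader of the study report could not tell from the plan how far off the number is, or in which direction.

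**Working it through.** The documents state no Vss/F, MRT or volume figure, so there is none to reproduce. The check has two parts.

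**1. The absorption term alone**

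Inputs: Protocol 3.2 says "Peak concentrations were observed at 1 to 2 days postdose, and the half-life was approximately 5 days". I take tmax as 24 to 48 h and half-life as 120 h. One-compartment disposition with first-order absorption is my assumption.

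- Elimination rate: k = ln 2 / 120 = 0.005776 per h.
- MRT of disposition: 1/k = 173.1 h.
- Absorption rate ka solves tmax = ln(ka/k) / (ka − k).
- Mean absorption time: MAT = 1/ka.
- MRT from subcutaneous data: 1/k + 1/ka.
- Relative excess in CL/F x MRT: MAT / (1/k) = k/ka.

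| tmax (h) | ka (per h) | MAT (h) | Subcutaneous MRT (h) | Excess |
|---|---|---|---|---|
| 24 | 0.1380 | 7.2 | 180.4 | 4.2% |
| 36 | 0.0781 | 12.8 | 185.9 | 7.4% |
| 48 | 0.0513 | 19.5 | 192.6 | 11.3% |

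Varying the half-life from 96 to 144 h widens the range to about 3% to 16%.

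**2. The number that would be tabulated**

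I applied the planned profile (predose, 8, 24, 48, 72 and 168 h, from the Schedule of Activities) to the titration doses. I used the linear rule up to tmax, the log rule after it, the last three points for the terminal slope, and the predicted last concentration. Kinetics are as in part 1. The table shows the ratio to the true Vss/F over tmax 24 to 48 h, without random error. The SAP states none of these three formulas.

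| Formula assumed | Day 1 | Days 50, 106 and 162 |
|---|---|---|
| Extrapolated: Dose/AUC(0-inf) x AUMC(0-inf)/AUC(0-inf) on Day 1; later Dose/AUC(0-168) x [AUMC(0-168) + 168 x (AUC(0-inf) − AUC(0-168))]/AUC(0-168) | 1.06 to 1.18 | 1.07 to 1.22 |
| Truncated at 168 h: Dose/AUC(0-168) x AUMC(0-168)/AUC(0-168) | 0.74 to 0.85 | 0.43 to 0.46 |
| Single-dose infinity formula used on later days | not applicable | 0.64 to 0.67 |

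The first row exceeds the 4% to 11% of part 1 partly because sampling is sparse. On Day 1 about 40% to 47% of AUC and 75% to 80% of AUMC is extrapolated, so the result leans heavily on the terminal slope.

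With 5% to 15% random error on concentrations and the first-row formulas, 59% to almost 100% of individual values exceeded the truth.

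With illustrative two-compartment models (assumed parameters, terminal half-life 120 h) and the first-row formulas, the ratio ran from 0.84 to 1.39. The absorption term is still positive in these models, but a slope fitted over 48 to 168 h can be too steep and outweigh it.

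**The case against.** A reader might infer that Vss/F would be too large on every profile day. The documents do not support that. The absorption term is always positive, but the sign of the net error depends on a formula the SAP does not give. Two of the three formulas above give values that are too small, and so do some of the two-compartment examples.

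A reader might also infer that a biased Vss/F would distort comparisons with other populations or feed into modelling. Neither use is stated. Protocol 10.3.3.1 allows a model-based analysis combined with other studies but names no noncompartmental volume as an input. The effect would also be hard to see: across the protocol's own tmax range, the largest shift between groups from absorption is 1.113/1.042, about 7%. With about 10 tirzepatide patients per cohort and an assumed between-patient CV of 20% to 40% (not in the documents), the 95% interval for a mean is about ±14% to ±29% (2.262 x CV / √10).

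Other points on that side:

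- Vss/F is not an endpoint, the PK summaries are descriptive, and parameters are determined only when possible. This stands, and it limits the severity.
- Vz/F is not a like-for-like replacement. It equals Vss/F only under one-compartment disposition, and it too depends on the terminal slope. This stands, and the fix has to say so.
- A formula or footnote may sit in the TFL shells or in the sponsor's style guide, which SAP 9.3.1 cites for formatting. This cannot be excluded. It would settle the formula, but it could not remove absorption time from subcutaneous data.
- The definition already says apparent and extravascular. That signals unknown bioavailability (the F in the label), not absorption time in the MRT.

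**Conclusion.** The point holds as a low-severity item. SAP 9.3.1 lists a parameter that subcutaneous data alone cannot deliver and does not say how it will be calculated. The absorption term adds about 4% to 11%, given the protocol's tmax and half-life and one-compartment first-order kinetics; the range is 3% to 16% if the half-life lies between 96 and 144 h. The net error in the tabulated value is undetermined in direction as well as size, because it also depends on the unstated formula and on the terminal slope. AUC, Cmax and CL/F do not use residence time and are not affected; nor is the primary endpoint, the incidence of treatment-emergent adverse events.

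**What to change.** Either of two changes to the SAP is enough.

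1. Delete the Vss/F row from the table in SAP 9.3.1 and its entry in SAP 2, and keep the already listed Vz/F as the apparent volume. Add a note that Vz/F is a terminal-phase volume and differs from a steady-state volume if disposition is multi-compartment.
2. Keep the quantity, but state its formula for Day 1 and separately for Days 50, 106 and 162, including whether MRT is truncated or extrapolated. Label it CL/F x MRT (includes absorption time), not Vss/F.

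The first is simpler and still meets Protocol 10.3.3.1, which mentions only an optional apparent volume, so no protocol amendment is needed. The cost is one table row, one abbreviation and any matching entry in the TFL shells. The second costs a few lines of text and a changed label.
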